We will use an intention-to-treat approach for all analyses. We plan to randomize 188 individuals (including both UCLA and VA sites), of whom we expect 13% to drop out (i.e., fail to complete study assessments) by 6-months, yielding N=164 participants with complete data (~ 82 per group). *We base this drop-out on our completed study ([name] VA Merit 08-295)*. We will include terms for stratification characteristics in all of the models. All analyses below assume $\alpha=0.05$, power=0.80, and two-sided hypothesis tests. Effect sizes are in the measure's natural units and Cohen's d (large=.8; medium=.5; small=.2).

- ***H1: Dysfunctional Beliefs and Attitudes About Sleep – Medication Scale ratings will improve with MTcap compared to SGT+CBTI post-treatment and at 6 months follow-up:***

Analysis: We will fit a 2 (group) by 3 (time) mixed model analysis of variance (ANOVA) model. Interaction terms will be used to assess the change in DBAS medication item (from baseline→post-treatment, baseline→6 months) for MTcap vs. SGT+CBTI group. **Power Analysis:** Based upon our prior research, we estimate the correlation of DBAS scores from baseline to 6-months will be $r=0.55$ (95% CI=0.42-0.65) and the standard deviation will be 2.1. Assuming n=82 per group, the study could detect an effect of 0.9 units on the DBAS-16 scale (Cohen's $d=0.43$). If the baseline to follow-up correlation is $r=0.42$ (95% lower confidence limit [LCL]), the detectable effect size is 1.0 unit on the DBAS-16 scale (Cohen's $d=.47$).

- ***H2a: Participants who receive MTcap will have increased likelihood of hypnotic discontinuation post-treatment and at 6 months follow-up compared with those who receive SGT+CBTI:***

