SGT+CBTI: The logistic regression models' dependent variable will be hypnotic discontinuation (yes=1/no=0 at post-treatment and 6-month follow-up) and the primary predictor of interest will be treatment group assignment (MTcap vs. SGT+CBTI). **Power Analysis:** We estimate that the SGT+CBTI group will have 60% discontinuation (based on prior studies = 59% to 63%, and our CBTI clinic's quality improvement data = 58% see "Technical Preliminary Studies"). We posit that a discontinuation percentage for the MTcap would need to be 80% (i.e., 20% greater) to be clinically meaningful. With an analytic sample size of n=82 per group, the study could detect a 20% difference in hypnotic discontinuation rate between groups (SGT+CBTI 60% vs. MTcap 80%). If the discontinuation rate of SGT+CBTI exceeds 60%, the study can detect even smaller differences (e.g., 17.8% difference if SGT+CBTI discontinuation rate is 70%). Even if the discontinuation percentage for the SGT+CBTI group is 50%, the study could detect a 21.3% difference (SGT+CBTI 50% vs. MTcap 71.3%). In our feasibility study, masked tapering resulted in 100% hypnotic discontinuation at post-treatment.

- ***H2b: Participants who receive MTcap will use less hypnotic post-treatment and at 6 months follow-up compared with those who receive SGT+CBTI:*** **Analysis:** Two outcomes will be

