assessed: frequency (i.e., days used, 0 to 7) and quantity (i.e., average daily dose in diazepam milligram equivalents). For each outcome, we will fit a 2 (group) by 3 (time) mixed model analysis of variance (ANOVA). Interaction terms will be used to assess the change in the outcome (from baseline→post-treatment, baseline→6 months) for MTcap vs. SGT+CBTI. **Power Analysis:** For these calculations, we use statistics from our recent study, which found a baseline to 6-month correlation of $r=0.83$ (95% CI=0.77-0.88) and a standard deviation of 1.94 for a similar outcome measure—“days used of medications commonly used for insomnia” (days used, 0 to 7 days). Assuming $r=0.83$ and $n=82$ per group, we could detect a treatment effect of 0.5 ($d=0.26$) (i.e. a discontinuation rate of half a day more for MTcap vs. SGT+CBTI group). Assuming $r=0.77$ (i.e., using the LCL), we could detect a treatment effect of 0.6 days ($d=0.31$). If we disregard these prior data, power calculations still show that we could detect a treatment effect of Cohen's $d=.44$ with $n=82$ per group. For quantity of use, power calculations indicate that we could detect a treatment effect of $d=0.44$ with $n=82$ per group.

- ***H3: Insomnia Severity Index scores will be lower with MTcap compared to SGT+CBTI at 6 months follow-up.*** **Analysis:** Similar to H2, we will fit a mixed model ANOVA, and an interaction term will assess the change in ISI from baseline to 6 months for MTcap vs. SGT+CBTI. **Power Analysis:** Based on prior research, we found the standard deviation (SD) and “baseline-to-6 month follow-up” correlation of ISI scores to be $SD=5.3$ and $r=0.39$ (95% CI=0.24-0.52), respectively. Assuming $r=0.39$ with a sample size of $n=82$ per group, the study could detect an effect of 2.56 units on the ISI (or a Cohen's $d=0.48$). Assuming $r=0.24$ (i.e., using the LCL), we could detect an effect of 2.86 units on the ISI (or a Cohen's $d=0.54$). These power analyses suggest that the study could detect effects that are medium sized (i.e., $d=0.48$, $d=0.54$).

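### H2a's logistic models leave out baseline dose and nights of use, which the trial already collects; the stated power is right, so this is a missed efficiency and not an error

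*Combined protocol and SAP*

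**What the plan says.** The section Primary data analysis plan and power analyses sets one covariate rule for every hypothesis: "We will include terms for stratification characteristics in all of the models". Under Randomization, the stratification factors are half-life class of the baseline drug (three levels) and gender.

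For H2a the outcome is discontinuation, yes or no, at post-treatment and at 6 months, and "the primary predictor of interest will be treatment group assignment (MTcap vs. SGT+CBTI"). No further covariate is named. The power paragraph uses a plain comparison of two proportions: "We estimate that the SGT+CBTI group will have 60% discontinuation", 80% under MTcap is taken as the clinically meaningful target, and "With an analytic sample size of n=82 per group, the study could detect a 20% difference in hypnotic discontinuation rate between groups". The general settings are a 5% significance level, "power=0.80, and two-sided hypothesis tests".

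Baseline use is recorded in several places before randomisation:

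- The telephone screen (Recruitment, Step 2) asks on how many days per week the hypnotic is taken.
- The baseline assessment (Step 3) includes a medication log kept during one week of actigraphy.
- The exclusion criteria need a baseline dose in diazepam equivalents, because more than 8 mg per night excludes.

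H2b then analyses "frequency (i.e., days used, 0 to 7) and quantity (i.e., average daily dose in diazepam milligram equivalents"), with baseline as one of its three time points.

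**The concern.** H1, H2b and H3 bring in the baseline value of their own outcome through the time factor. H2a cannot, because entry requires current use and so everyone is a non-stopper at baseline. It is therefore the one hypothesis test whose model holds no information on how much hypnotic a participant was using at the start.

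That starting point varies. Entry runs from two nights a week up to nightly use, at any dose up to the cap. The protocol itself treats dose as relevant to withdrawal: high doses are excluded to reduce risk, and as-needed users get their own taper schedule. It is plausible that lighter users stop more easily.

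Two things are at stake. The first is precision: H2a sits at almost exactly 80% power for the difference the sponsor calls clinically meaningful, and adjusting for a prognostic covariate raises power in a logistic model. The second is chance imbalance, because neither dose nor nights is a stratification factor. If the arms differed on either, an adjustment added after the data were seen would be open to the charge of selection.

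**Working it through.** **Inputs from the documents.** 188 randomised, 13% dropout, 82 per arm analysed, 60% versus 80%, two-sided 5%, target power 80%.

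**Input that is assumed.** The strength with which baseline dose or nights predicts stopping. The documents give no value, so a range is shown.

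**Step 1: reproduce the plan's figure.**

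188 × 0.87 = 163.6, so 164, or 82 per arm.

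Pooled-variance sample size, with mean proportion 0.70:

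n = [1.96·√(2·0.70·0.30) + 0.8416·√(0.60·0.40 + 0.80·0.20)]² / 0.20² = (1.2702 + 0.5323)² / 0.04 = 81.2, so 82 per arm.

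Power at 82 = Φ[(0.20·√82 − 1.2702) / 0.6325] = Φ(0.855) = 80.4%.

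The two alternatives in the plan also reproduce at 82 per arm: 70% versus 87.8% and 50% versus 71.3% each give 80.3%. The power statement is right as written.

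**Step 2: change in power against the plan's own model.** Trials were simulated with 82 per arm and stopping fixed at 60% and 80%. Each data set was analysed with treatment plus strata, and again with baseline covariates added. The table gives the paired change from two separate runs. Run B used 8,000 trials per scenario, with one prognostic and one null covariate added.

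| Assumed log-odds per SD | Odds ratio per SD | AUC of covariate for stopping | Run A (points) | Run B (points) |
|---|---|---|---|---|
| 0 | 1.00 | 0.50 | −0.1 | −0.1 |
| 0.4 | 1.49 | 0.61 | +1.3 | +1.0 |
| 0.6 | 1.82 | 0.66 | +2.3 | +2.4 |
| 0.8 | 2.23 | 0.70 | +4.3 | +4.2 |
| 1.0 | 2.72 | 0.74 | +5.7 | +5.4 |

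For scale, at log-odds 0.6 run B moved from 80.9% to 83.3%.

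**Step 3: both covariates prognostic.** A further simulation (5,000 trials per scenario, Wald tests) let dose and nights, correlated 0.4, contribute to a joint score. R² is on the probability scale in the control arm.

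| Odds ratio per SD of score | R² | Strata only | Plus dose and nights |
|---|---|---|---|
| 1.00 | 0 | 79.5% | 79.6% |
| 1.35 | 0.02 | 79.8% | 80.1% |
| 1.65 | 0.05 | 80.6% | 82.2% |
| 2.12 | 0.11 | 79.6% | 83.6% |
| 2.72 | 0.17 | 79.9% | 85.2% |

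Each power figure has a Monte Carlo standard error of √(0.8·0.2/5000) = 0.6 points. The strata-only column therefore varies by chance, and the within-row differences are what matter.

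**Step 4: cross-check by effective sample size, n/(1 − R²).**

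- R² 0.05: 82/0.95 = 86.3 per arm, power 82.4%, detectable difference from 60% of 19.5 points.
- R² 0.10: 82/0.90 = 91.1 per arm, power 84.4%, detectable difference 19.0 points.
- With no covariate the detectable difference is 19.9 points.

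This agrees with the simulations.

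**Step 5: error rate and imbalance.** In 6,000 null trials a covariate-adjusted logistic test rejected in 4.9%. The standard error of a standardised baseline difference is √(2/82) = 0.156. A difference beyond 0.2 SD is 0.2/0.156 = 1.28 standard errors, which for any one covariate happens in about 1 trial in 5.

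**The case against.** The strongest reply is that nothing here is wrong. The plan meets its 80% target without these covariates, and a trial at conventional power is not defective for lacking a margin. That stands. A reader might infer that H2a is underpowered or its sample size miscalculated; Step 1 shows neither.

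Second, the benefit rests on a strength the documents do not supply, and the design may weaken it. The planned reduction is proportional, about 25% a week. As-needed users start from their own weekly total. The entry limits narrow the range of dose and nights. Average daily dose also partly contains nights, so the two covariates overlap. All of this stands, and it is why the range starts at zero.

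A tempting way to fill the gap is the baseline to 6-month correlation of 0.83 in the H2b power paragraph. Read as a latent correlation between baseline use and stopping, it would take simulated power from 79.9% to 96.0%. The documents do not support that reading. The figure comes from another study and describes days of use of medications commonly used for insomnia, not yes/no stopping after a supervised taper.

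Third, H2b already uses baseline nights and dose. That is true, but it does not adjust the H2a test.

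Fourth, calling treatment the primary predictor leaves room for other terms, and H2a's analysis text lacks the label its neighbours carry, so some words may be missing from the public copy. That is possible but not shown. As the text stands, no further covariate is pre-specified.

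Finally, adjustment is not free: a non-prognostic covariate can cost a few tenths of a point, and the odds ratio becomes conditional.

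**Conclusion.** The point holds as a missed efficiency. H2a is specified with treatment and the stratification terms only, although two plausibly prognostic baseline measures will be in hand before randomisation. The gain over the plan's strata-adjusted model is about 0 points if they are not prognostic, and roughly 1 to 6 points for an assumed log-odds of 0.4 to 1.0 per SD. The direction is secure; the size depends wholly on that assumption. The trade is favourable because the possible loss is a few tenths of a point at most. Pre-specification also settles in advance how a chance imbalance in starting use is handled.

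**What to change.** In both H2a models, post-treatment and 6 months, pre-specify baseline average daily dose (diazepam-equivalent mg) and baseline nights of use per week as covariates alongside half-life class and gender. State which baseline source supplies each value (screening interview, medication log or record review) and that both enter as continuous terms.

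From the same model, report the standardised stopping percentage in each arm and their difference with a confidence interval. The adjusted odds ratio is conditional and does not map directly onto the plan's 60% versus 80% target; the standardised figures do. The sample size statement can stay as it is.

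The cost is a short SAP addition made before the outcome data are examined, two extra degrees of freedom, and one added summary per time point. No new data collection or change in trial conduct is needed.

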Title: Sleep Without Insomnia or The Use of Chronic Hypnotics (SWITCH)

PI: [name], MSHS

NCT number: NCT03687086

Document date: June 19, 2020

SWITCH STUDY PROTOCOL (06.19.2020)

[APPENDIX: "Video/Telehealth Visit Addendum to SWITCH Study Protocol" is at end of document](#)

Design

This is a 5-year multi-site randomized controlled trial that will recruit participants from UCLA Health System and VA Greater Los Angeles.

Setting: To ensure that we meet enrollment targets, the study will include both VAGLA and UCLA Health System. At least 1,200 unique patients at VAGLA have the targeted hypnotics listed in their medical records for at least 3 months within the past 6 months, and 9,100 unique patients at UCLA Health System who receive primary or medicine subspecialty care in the northwest Los Angeles UCLA Health System outpatient clinics have the targeted medications listed within 12 months.

Inclusion/Exclusion criteria:

Inclusion criteria:

- Age > 55 years
- Use of lorazepam, alprazolam, temazepam, clonazepam and/or zolpidem for current or prior insomnia symptoms 2 or more nights per week for at least 3 months
- Current or prior insomnia symptoms
- Available to attend weekly in-person or video sessions over 9 weeks

Exclusion criteria:

High risk for complications in outpatient hypnotic discontinuation program:

- Seizure disorder
- Supratherapeutic or high baseline hypnotic dose (> diazepam-equivalent of 8 mg/night). Note that for individuals on > 1 of the targeted hypnotics, the total baseline hypnotic dose in diazepam-equivalents will be calculated and if > 8 mg/night, individual will be excluded.
- High baseline risk of complicated withdrawal; benzodiazepine intoxication or current or past symptoms of complicated benzodiazepine/alcohol withdrawal (e.g., seizure, delirium at baseline (prior to taper))
- Polydrug use (e.g., chronic high dose opioids)
- Unable to keep study medications in secure location
- Evidence of prescription fraud (e.g., multiple prescriptions for same drug filled at UCLA and non-UCLA pharmacies, diversion)

Discontinuation of hypnotic not appropriate:

- Study-targeted hypnotic used to treat another clinical condition (e.g., panic disorder)

Poor candidate for CBTI:

- Presence of bipolar disorder
- Cognitive impairment (e.g., Mini-Mental State Examination < 24)

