 - International Classification of Sleep Disorders 3 diagnostic criteria for insomnia questions
 - Nighttime urinary symptoms questions
- Blood pressure, pulse and respiration will be measured
- A wrist actigraph will be given to participants to wear at home for 1 week
- A sleep diary and a medication log will be given to participants to complete while wearing the actigraph.
- Screening for sleep apnea – all participants will be administered the STOP-Bang questionnaire to screen for symptoms of sleep apnea. If a participant scores > 4 on the STOP-Bang and does not have documentation of a previous sleep study in the medical record, s/he will be sent home with a portable sleep apnea screening device (WatchPAT) to wear for one night and to return the next day. The WatchPAT is an FDA approved device and is used clinically for in-home screening for sleep apnea. Participants will be instructed how to attach the sensors and will wear the device for one night. The PI or one of the MD co-investigators will talk with the participant about the results of the test. The results will be shared with the participant's healthcare provider if requested by the participant.
- Hypnotic medication log - Using a structured hypnotic abstraction form (see Hypnotic Abstraction Form), we will review the UCLA electronic record to obtain data about hypnotic prescriptions. We will also query the California Controlled Substance Utilization Review and Evaluation System (CURES) database to obtain data about non-UCLA hypnotic prescriptions.

Eligibility determination for randomization

The final determination of eligibility will take place during a weekly meeting of the investigators. At least one physician ([name] or [name]) and at least one sleep psychologist (e.g., [name]) will participate at these meetings. During this “pre-randomization review” meeting, individuals who no longer meet the hypnotic criteria at the baseline assessment will be excluded. Individuals adherent to sleep-disordered breathing therapy and restless legs syndrome (RLS) therapy or with insomnia symptoms incompletely explained by RLS will be considered for intervention, as would be done in clinical practice. Individuals with insomnia symptoms due to circadian rhythm sleep disorders or inadequate opportunity for sleep will be excluded.

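### H2b's detectable differences of 0.5 and 0.6 days hold only at a borrowed correlation that H2a's stopping rates make hard to reach without an unstated dependence, and its d=0.44 needs a correlation of about 0.5 that the plan does not state

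*Combined protocol and SAP*

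**What the plan says.** All points are in the section on the primary data analysis plan and power analyses, unless another section is named.

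- **H2b, analysis.** Frequency (days used, 0 to 7) and quantity (diazepam-equivalent daily dose) are each fitted with a group-by-time mixed model. "Interaction terms will be used to assess the change in the outcome" from baseline to post-treatment and to 6 months.
- **H2b, power for frequency.** The correlation of 0.83 (95% CI 0.77 to 0.88) and SD of 1.94 come from an earlier study of a similar measure. With 82 per group the plan gives 0.5 days (d=0.26), which it explains as "i.e. a discontinuation rate of half a day more for MTcap vs. SGT+CBTI group", and 0.6 days (d=0.31) at r=0.77.
- **H2b, fallback and quantity.** "If we disregard these prior data, power calculations still show" a detectable d of 0.44. The same 0.44 is given for quantity. Neither figure comes with a correlation or an SD.
- **H2a.** The planning rates are 60% stopping under SGT+CBTI and 80% under MTcap, with alternatives of 50% against 71.3% and 70% against a rate 17.8 points higher (87.8%).
- **Inclusion criteria and the eligibility determination before randomization.** Entry requires hypnotic use "2 or more nights per week for at least 3 months", and this is checked again: "individuals who no longer meet the hypnotic criteria at the baseline assessment will be excluded".

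**The concern.** H2a and H2b describe the same participants, but their planning inputs are not linked. Everyone enters using a hypnotic on at least 2 nights a week. Under H2a most then stop, so if stopping means zero days, most follow-up values are zero whatever the baseline was. That pulls the baseline-to-follow-up correlation down, while the 0.5- and 0.6-day figures need it to be high.

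The correlation matters because the planned test is on change from baseline. When r is below 0.5 and the SDs are equal, change is noisier than the follow-up value alone. A null H2b result could then be read as excluding a half-day difference that the test was not able to detect. For quantity of use, the d=0.44 without an r is the only power statement in the plan.

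**Working it through.** **Inputs from the plan:** 82 analysed per group, two-sided 0.05, power 0.80; SD 1.94; r=0.83 and 0.77; H2a's stopping rates.

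**1. Reproducing the plan.** For a plain two-group comparison the detectable d is (1.960+0.842)×√(2/82) = 0.438, or 0.440 by noncentral t. For change from baseline with equal SDs, d in raw-SD units is 0.440×√(2(1−r)).

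| r | detectable d | days at SD 1.94 | plan |
|---|---|---|---|
| 0.83 | 0.257 | 0.498 | 0.5 |
| 0.77 | 0.299 | 0.579 | 0.6 |

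The same formula reproduces H1 and H3 to rounding.

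**2. Ceiling on r under H2a.** Write follow-up days as Y = B×W, where B=1 for those who continue (probability q) and 0 for those who stop, and W is use among continuers. Assume B is independent of baseline use X and of W. Then

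- Cov(X,Y) = q·Cov(X,W) ≤ q·SD(X)·SD(W)
- Var(Y) = q·Var(W) + q(1−q)·E(W)² ≥ q·Var(W)

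so r ≤ √q for any baseline distribution and any use among continuers.

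| stopping rates (SGT+CBTI / MTcap) | ceiling on r |
|---|---|
| 60% / 80% | 0.63 / 0.45 |
| 50% / 71.3% | 0.71 / 0.54 |
| 70% / 87.8% | 0.55 / 0.35 |

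All lie below 0.77. At 60%/80% the mean ceiling is 0.540, and 0.440×√(2×0.460)×1.94 = 0.82 days. This is a lower limit for SD 1.94 at both times.

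**3. Can dependence on baseline use restore r?** Let the lightest users stop first, the strongest form of dependence. The highest r found was 0.88 (60% arm) and 0.69 (80% arm) for use spread evenly over 2 to 7 nights; 1.00 and 0.85 if most use 2 nights; and 0.57 and 0.35 if 60% use nightly. So it can for some baselines and not for others.

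**4. Unit and meaning of d=0.44.** Wherever the section gives an SD, d is the raw difference over the raw SD: 0.5/1.94=0.26, 0.6/1.94=0.31, 0.9/2.1=0.43, 2.56/5.3=0.48, 2.86/5.3=0.54. In those units 0.44 is the plain two-group value, and it equals the change-contrast value only at r=0.5 (about 0.49 allowing for rounding).

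| r | detectable d, change contrast | power for d=0.44 |
|---|---|---|
| 0.5 | 0.44 | 80% |
| 0.24 | 0.54 | 62% |
| 0 | 0.62 | 51% |

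H3, with the same n and contrast, reports 0.48 at r=0.39 and 0.54 at r=0.24.

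**5. Power for the difference H2a implies.** The documents give neither baseline nights nor continuers' use, so this step rests on assumptions. As one example, take baseline mean 5 (assumed), SD 1.94, stopping unrelated to baseline, and continuers keeping all their nights.

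- Implied difference: 0.2×5 = 1.0 day.
- Variance of change, p·SD²+p(1−p)·mean² with p the stopping rate: 8.26 and 7.01. SE = √(15.27/82) = 0.432; detectable difference 2.802×0.432 = 1.21 days; power Φ(1/0.432−1.96) = 64%.
- Baseline-adjusted: follow-up variances are 7.51 and 4.75 (mean 6.13) and the common slope is 0.3. Residual variance = 6.13−0.09×3.76 = 5.79; SE = √(2×5.79/82) = 0.376; power Φ(1/0.376−1.96) = 76%.

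The wider check used six illustrative baselines on 2 to 7 nights (means 3.95 to 6.70), with continuers keeping 50 to 100% of their nights and each baseline's own SD.

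| relation of stopping to baseline use | power, change | power, adjusted |
|---|---|---|
| none | 28–78% | 73–80% |
| each extra night cuts odds of stopping by about 40% | 48–81% | 81–83% |
| stronger | 69–99% | 82–99% |

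In the first row r is 0.07 to 0.32, the detectable difference 0.77 to 1.37 days, and the implied difference 0.40 to 1.34 days. The 0.77 lies below the 0.82 of step 2 only because some of these baselines have a different SD.

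**The case against.** The plan is open about its source: it calls the earlier measure similar, uses the lower confidence limit as well, and adds a figure that sets the prior data aside. Whether r=0.83 carries over cannot be judged without that study. The ceiling in step 2 applies only if stopping means zero days and is unrelated to baseline use, and it is quite natural that heavier users stop less often. All of this stands. It means that the plan leaves a needed assumption unstated, not that it has made an error.

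A reader might infer that the half-day sensitivity contradicts H2a outright. The documents do not support that: they give no baseline distribution, and for some distributions strong dependence brings r close to or above 0.77. A reader might also infer that the fallback, 0.85 days at SD 1.94, is nearer to what H2a implies. That does not hold in general. If stopping is unrelated to baseline and continuers halve their nights, the implied difference is 0.2×0.5×mean, or 0.395 to 0.67 days for means of 3.95 to 6.70, which is nearer to 0.5–0.6.

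On d=0.44, the plan does not name the SD behind Cohen's d. If d were in SDs of change, 0.44 would be right at any r. The raw-SD reading is an inference, though every figure in the section with a stated SD agrees with it.

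Finally, the change-from-baseline interaction is a valid test and is used consistently across H1, H2b and H3. The case for adjustment is one of power, not validity.

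**Conclusion.** The point holds in conditional form and is worth fixing. The 0.5- and 0.6-day figures are correct arithmetic on borrowed inputs. If discontinuation means zero days and stopping is unrelated to baseline use, the detectable difference at SD 1.94 is at least about 0.82 days. An r of 0.77 to 0.83 would need heavier users to continue more often, which the plan does not state and which reaches that r only for some baselines.

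If d is in raw-SD units, the two d=0.44 statements have 80% power under the planned contrast only when r is about 0.5 or more.

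The practical cost depends on assumptions that the documents cannot settle. With stopping unrelated to baseline use, the change contrast may lose a good deal of power relative to an adjusted one. The gap narrows, and the change contrast can exceed 80%, when dependence is strong.

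It might be inferred that the trial is too small or its H2b estimates biased. Neither follows: H2a's own calculation gives 82 per group (80.4% power at 60% against 80%), and the choice of contrast affects precision only.

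**What to change.** For both H2b outcomes, test a baseline-adjusted contrast, either with baseline as a covariate or with baseline means constrained equal in the mixed model. The residual SD is then the follow-up SD times √(1−r²), so d=0.44 in follow-up SD units holds at any r. If the change contrast is kept, state 0.44 as conditional on r of about 0.5 or more in raw-SD units, and add 0.62 at r=0.

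In either case, define discontinuation in terms of days used and label the 0.5- and 0.6-day figures as conditional on the borrowed r and SD. Beside them, give a range under H2a's stopping rates, with the assumed baseline nights, continuers' use and relation of stopping to baseline use, and with power at the implied differences. It would also help to reword the half-day gloss as a difference in mean days used, since it is not a discontinuation rate.

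The cost is a reworded power paragraph with a less favourable frequency figure and, for the preferred option, a small model change using a baseline value already collected. The 188 randomized and about 82 analysed per group stay as they are.

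### H1, H2b and H3 test change from baseline through a group-by-time interaction, which loses precision at the plan's own correlations; for the ISI it is less precise than ignoring baseline.

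*Combined protocol and SAP*

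**What the plan says.** The section on the primary data analysis plan and power analyses specifies a 2 (group) by 3 (time) mixed-model ANOVA for H1 and H2b, and a similar model for H3. The test is the interaction in each case:

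- H1: "Interaction terms will be used to assess the change in DBAS medication item", from baseline to post-treatment and from baseline to six months.
- H2b (days used and average daily dose): "Interaction terms will be used to assess the change in the outcome", over the same two intervals.
- H3: "an interaction term will assess the change in ISI from baseline to 6 months for MTcap vs. SGT+CBTI".

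On covariates the plan says only this: "We will include terms for stratification characteristics in all of the models". According to the Randomization section, these characteristics are hypnotic half-life class and gender. Neither the baseline value of the outcome as a covariate nor a common baseline mean is mentioned. For H3 the power paragraph states that, at r=0.39, "the study could detect an effect of 2.56 units on the ISI", and gives 2.86 units at r=0.24. The telehealth addendum leaves the analysis plan unchanged.

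**The concern.** When each arm has its own baseline mean, the group-by-time interaction is the difference between arms in mean change. Subtracting baseline removes between-person variation but also brings in the noise of the baseline measurement. If baseline and follow-up are only weakly correlated, the second effect outweighs the first. Randomization makes the true baseline means equal, so nothing is gained by estimating them separately. A model that uses this fact weights baseline by how well it predicts follow-up, and does at least as well at any correlation.

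The plan's numbers already show the loss. For ISI it needs d=0.48, or 0.54 at the lower confidence limit. Under H2b, where it sets prior correlation data aside, it quotes d=0.44, which is what a plain follow-up comparison of 82 with 82 can detect. Power is therefore given up on three of the four hypotheses although baseline is collected anyway, and a real but modest ISI benefit becomes more likely to be missed.

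**Working it through.** **Inputs, all from the power section.** Two-sided α=0.05 and 80% power; 188 randomized with 13% dropout (188 × 0.87 = 163.6), giving about 82 per group. Baseline to six-month correlations and SDs: ISI SD 5.3, r=0.39 (95% CI 0.24 to 0.52); DBAS SD 2.1, r=0.55 (0.42 to 0.65); days used SD 1.94, r=0.83 (0.77 to 0.88). One SD is given per outcome, so equal SDs at baseline and follow-up are assumed, as in the plan.

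**Formula.** Detectable effect = (1.960 + 0.842) × SD × √f × √(2/82) = 0.4375 × SD × √f. The variance factor f is:

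- change from baseline (the interaction): f = 2(1−r)
- six-month score only: f = 1
- baseline-adjusted: f = 1−r²

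**Reproducing the plan.** ISI, r=0.39: f=1.22, so 0.4375 × 5.3 × 1.1045 = 2.561 (stated 2.56). ISI, r=0.24: f=1.52, giving 2.859 (stated 2.86). DBAS: 0.872 and 0.990 (stated 0.9 and 1.0). Days used: 0.495 and 0.576 (stated 0.5 and 0.6). The set as a whole matches the change-score formula.

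**Detectable effects under the three analyses.**

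| Outcome | r | Change (planned) | Follow-up only | Baseline-adjusted |
|---|---|---|---|---|
| ISI | 0.39 | 2.561 | 2.319 | 2.135 |
| ISI | 0.24 | 2.859 | 2.319 | 2.251 |
| ISI | 0.52 | 2.272 | 2.319 | 1.981 |
| DBAS | 0.55 | 0.872 | 0.919 | 0.767 |
| DBAS | 0.42 | 0.990 | 0.919 | 0.834 |
| Days used | 0.83 | 0.495 | 0.849 | 0.473 |
| Days used | 0.77 | 0.576 | 0.849 | 0.542 |

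Using the noncentral t instead of the normal approximation raises the ISI row at r=0.39 slightly, to 2.58, 2.33 and 2.15.

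**Power at an ISI effect of 2.56 units.** At r=0.39: 80.0% planned, 87.1% follow-up only, 91.9% adjusted. For 80% power at that effect, the three analyses need 83, 68 and 58 per group. At r=0.24 the standard errors are 5.3 × √1.52 × √(2/82) = 1.020 planned and 5.3 × √0.9424 × √(2/82) = 0.804 adjusted. Power is then about 71% and 89%.

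**Power at a true ISI benefit of 2 points, r=0.39** (an illustrative value; the plan names no ISI target). The standard errors are 0.914 planned and 0.762 adjusted, so power is Φ(2/0.914 − 1.96) = 59% and Φ(2/0.762 − 1.96) = 75%.

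**Equivalent sample size.** The variance ratio of change to adjusted is 2(1−r)/(1−r²) = 2/(1+r). For ISI this is 2/1.39 = 1.44, and 164 × 1.44 ≈ 236. For DBAS it is 2/1.55 = 1.29, and for days used 2/1.83 = 1.09.

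**Three-time-point model and dropout.** The generalized least squares information for the full model gives the same ISI values with complete data: 2.561 for the interaction and 2.135 with a common baseline mean. Then take 94 per group with 12 missing at six months. The plan gives no correlations involving the post-treatment visit, so baseline to post-treatment is assumed to be 0.39 and post-treatment to six months 0.39 to 0.70. The interaction detects 2.46 to 2.50 and the common-baseline model 2.08 to 2.13. The interaction still does worse than the follow-up-only comparison in 82 per group (2.319).

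**The case against.** The strongest reply is that nothing here is wrong. The interaction is a valid test under randomization, and the stated detectable effects are correct for it and openly reported. H2a, the discontinuation hypothesis, uses logistic regression and is untouched. All of this stands: the point is about efficiency, not bias or miscalculation.

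Several limits on size also stand.

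- For days used, the gain is only about 4% in detectable effect at r=0.83. For average daily dose the plan gives neither SD nor correlation, so the loss cannot be sized.
- The claim that change is worse than ignoring baseline needs r below 0.5 with similar SDs. It holds for ISI at 0.39 and 0.24 and for DBAS at its lower limit of 0.42. It fails for ISI at the upper limit of 0.52, for DBAS at its planning value of 0.55, and for days used.
- The DBAS figure of 0.9 alone does not identify the formula, because a follow-up-only comparison gives 0.919. The values that move with r do identify it.
- At a true ISI benefit of 2 points, the adjusted analysis would still miss about one trial in four.

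None of this favours the interaction. The adjusted analysis has the smaller detectable effect in every row of the table, and dropout leaves the order unchanged.

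**Conclusion.** The concern holds. At the plan's own correlations, testing H1, H2b and H3 through change from baseline gives up precision that the collected data would supply. The loss is large for ISI (detectable effect 2.56 against 2.14 at r=0.39; 2.86 against 2.25 at r=0.24), moderate for DBAS and small for days used. For ISI at the planning correlation, the planned contrast has 22% more variance than six-month scores alone and 44% more than the adjusted analysis.

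The sizes assume equal SDs at baseline and six months, and 82 analysed per group. If the SDs differ, the ISI ranking of change below follow-up-only at r=0.39 persists while the six-month SD is less than 1/(2 × 0.39) = 1.28 times the baseline SD. The advantage of adjustment over change does not depend on r being below 0.5. The change should be made, but the trial is not invalid without it.

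**What to change.** For H1, H2b and H3, keep the repeated-measures model but give both arms a common baseline mean: time as a categorical factor, group effects at post-treatment and six months only, no group term at baseline, the stratification terms, and an unstructured covariance matrix. Test the group contrast at six months for H3, and at both follow-ups for H1 and H2b. An acceptable alternative is a mixed model of the two follow-up scores with baseline and baseline-by-visit terms as covariates. Write this into the plan before outcomes are examined by arm.

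Restate the detectable effects using SD × √(1−r²): about 2.14 ISI units (2.25 at the lower limit of r), 0.77 DBAS units (0.83) and 0.47 days (0.54). For average daily dose, d=0.44 can stay as a conservative figure, since under adjustment and equal SDs it is the most that would be needed at any correlation.

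The cost is a change of wording in the analysis plan. It uses the same data, visits, participants and software.
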